4.5.1 Primary Outcome Measure

COVID-19 vaccine confidence. We will assess participants' confidence in the COVID-19 vaccines using an adapted version of the Vaccine Confidence Index (VCI)⁴⁹ for COVID-19. The COVID-19 VCI is a 3-item measure that assesses vaccine confidence across three domains: safety, effectiveness, and importance (see Table 3). Each item is rated on a 5-point scale ranging from 1 ('Strongly disagree') to 5 ('Strongly agree'). Participants will be considered 'confident' (score of '1') if they respond 'Agree' or 'Strongly agree' on all three items and 'not confident' (score of '0') if one or more item responses is not 'Agree' or 'Strongly agree'.

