P-values ≥ 0.0001 will be reported to 4 decimal places; p-values less than 0.0001 will be reported as " <0.0001 ". The mean, standard deviation, and any other statistics other than quantiles, will be reported to one decimal place greater than the original data. Quantiles, such as median, minimum, or maximum will use the same number of decimal places as the original data. Estimated parameters, not on the same scale as raw observations (e.g. regression coefficients) will be reported to 3 significant figures.

Adherence to interventions

Analysis of both intention-to-treat (ITT) and as-treated populations will be performed. All participants who are randomized to a trial arm will be included in the ITT analyses. Participants who adhere to major engagement criteria for their primary intervention will be included in the as-treated analyses.

Analysis methodology

Aim 1

To compare the impact of two interventions delivered online: 1) a dialogue-based webinar (webinar) using the existing COVID-19 Option Grid conversation aid and, 2) an interactive and, dynamic, and multi-component social media web application (social media website), compared to enhanced usual practice (link to Centers for Disease Control (CDC) vaccine website), on COVID-19 vaccine confidence (primary outcome), and other secondary outcomes among LTCWs. We hypothesize that each intervention will be superior to enhanced usual practice at increasing vaccine confidence (*Hypothesis 1.1*) and that the dialogue-based webinar intervention will be superior to the social media arm at increasing vaccine confidence (*Hypothesis 1.2*).

Corresponding analyses

Primary outcome

The primary outcome is the binary classifier of vaccine confidence derived from the three-item Vaccine Confidence Index (VCI), evaluated at 3 weeks post-randomization, which will be analyzed by randomization arm. The determined binary predictors of intervention outcomes will be compared using two-proportion z-tests to identify significant differences between each intervention and enhanced usual practice (Arm 1 vs Arm 3 & Arm 2 vs Arm 3 - superiority analyses) and between the intervention arms (Arm 1 vs Arm 2 - two-tailed equivalency analysis).

Secondary outcomes

- *Change from baseline in COVID-19 Vaccine Confidence.* Analysis of change from

baseline will be based on a binary classifier whether the average score increases (1) or does not increase (2) at T1, T2, and T3 versus baseline.

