- *Feeling informed about the COVID-19 vaccines*. The degree to which participants' feel informed about the COVID-19 vaccines (have enough information and understand that information) will be evaluated using a continuous variable, calculated as the mean scale

score across two items ((1) having enough information, (2) understanding the information) for each participant. The mean of all mean scores will be compared across trial arms with two-sample unpaired t-tests.

- *Identification of COVID-19 vaccine information and misinformation.* Subjects' identification of COVID-19 vaccine information and misinformation will be scored on a scale of zero to four and treated as a continuous linear variable. Results will be compared across trial arms with two sample unpaired t-tests.
- *Trust in COVID-19 information from different sources.* Subjects' trust in COVID-19 information from different sources will be evaluated using a continuous variable, calculated as the mean scale score across three items for each participant. The mean of all mean scores will be compared across trial arms with two-sample unpaired t-tests.
- *Change from baseline in secondary outcomes.* Change from baseline will be scored as a binary variable with an increased value scored as one and a no change or decreased value scored as zero. For each evaluation after baseline, each arm will be compared using two-proportion z-tests. For vaccine and booster intent questions, where the intent question is not repeated if the participant indicates an increase in vaccination status, intent will be imputed from uptake. To be clear, an individual who is unvaccinated at T0, then returns at T1 and indicates that he or she is now vaccinated, will be presented with the vaccine intent question at T0 but not at T1. Because the individual is now vaccinated, asking about vaccine intent at T1 would be confusing. For analyzing change in vaccine intent, the individual whose vaccine status increases would be considered to have positive intent at T1. A similar approach will be used for booster intent.
- *As treated analysis of primary and secondary outcomes.* Primary and secondary outcome analyses will be repeated, limited to the as treated samples.

Aim 2

To determine if LTCWs' characteristics and other factors mediate and moderate the interventions' impact on vaccine confidence and other secondary outcomes.

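### Scoring change from baseline as increased or not increased discards scale information and gives worsening no category; baseline-adjusted scores would use the same data better

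*Combined protocol and SAP*

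**What the plan says.** Appendix B, Secondary outcomes, contains two change rules.

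- VCI: a "binary classifier whether the average score increases (1) or does not increase (2) at T1, T2, and T3 versus baseline". This bullet names no test of its own.
- All other secondary outcomes: change is binary, "with an increased value scored as one and a no change or decreased value scored as zero". The test follows: "For each evaluation after baseline, each arm will be compared using two-proportion z-tests". I read this as also covering the VCI change, which is itself listed as a secondary outcome.

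Neither rule adjusts for the T0 value, deals with participants already at the maximum, or separates a fall from no change. The code for a score that did not increase is 2 in the first rule and 0 in the second.

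Elsewhere the plan keeps the scales:

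- VCI has three items (protocol section 4.5.1): "Each item is rated on a 5-point scale ranging from 1".
- Misinformation identification "will be scored on a scale of zero to four and treated as a continuous linear variable".
- Trust is "calculated as the mean scale score across three items for each participant", and feeling informed is the same kind of average over two items. For both at T1, "The mean of all mean scores will be compared across trial arms with two-sample unpaired t-tests".

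Under Multiple testing, Appendix B says that secondary results will be read in aggregate for their direction, with no corrected p-value threshold.

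**The concern.** The plan treats three outcomes as continuous when comparing arms at T1, then drops the scale when the same outcomes are compared as change at T1, T2 and T3. No reason is given. Three things follow from the rule itself.

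1. A one-step gain counts the same as a large gain. The average of three 1-to-5 items can take 13 values (sums 3 to 15), and the change in it is cut to two categories.
2. A participant at the top of the scale at T0 cannot be scored as increased, whatever the intervention does.
3. A fall is stored as no change, so an arm difference confined to falls does not enter the test.

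What is at stake is the evidence on whether any effect lasts to three and six months. For Aim 1, Appendix B specifies no other arm comparison at those times.

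**Working it through.** **Step 1. The plan's own figure.** Section 4.6 states 80% power for an 8-point difference with 600 per arm, two-sided 0.05, and 80% for 10 points after 40% attrition (600 × 0.6 = 360 per arm). The control rate is not stated, so I scanned it, using

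power = Φ[(δ√n − 1.96√(2p̄q̄)) / √(p₁q₁ + p₂q₂)].

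- 46% vs 54%, n = 600: (0.08 × 24.495 − 1.96 × 0.7071) / 0.7048 = 0.814, power 0.792.
- 45% vs 55%, n = 360: power 0.766.
- Both statements come within two points of 80% at control rates of about 33–35% or 55–58%.

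The figure therefore reproduces for the binary primary outcome. No power is stated for any change outcome.

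**Step 2. Normal-theory benchmark.** Splitting a normal change score near its median keeps 2/π = 0.637 of the information. An effect with 80% power on the numeric change has noncentrality 1.960 + 0.842 = 2.802. After the split it is 2.802 × √0.637 = 2.236, so power is Φ(2.236 − 1.960) = 0.61. Restoring 80% needs π/2 = 1.57 times the sample.

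**Step 3. Discrete scales.** I simulated latent-normal scores with a 0.25 SD shift, latent correlation 0.5 to 0.85 and several baseline levels, all assumed. One setting in full, for two items on an assumed 1-to-5 scale, latent correlation 0.85 and 35% at the ceiling:

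- Increased: 25.0% vs 34.1%. Effect per √n = 0.091 / √(0.25 × 0.75 + 0.341 × 0.659) = 0.142.
- Numeric change: 0.204. ANCOVA on T0: 0.221.
- Information kept: (0.142/0.204)² = 0.49 of numeric change; (0.142/0.221)² = 0.41 of ANCOVA.
- At 360 per arm: Φ(0.142 × 18.97 − 1.96) = 0.77 for the yes/no rule, Φ(0.221 × 18.97 − 1.96) = 0.99 for ANCOVA.

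Across settings, the information kept by the yes/no rule was:

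| Scale | vs numeric change | vs ANCOVA |
|---|---|---|
| 2–3 five-point items (4–35% at ceiling) | 0.45–0.65 | 0.31–0.58 |
| 0–4 misinformation, 3-level intent | 0.24–0.83 | 0.15–0.64 |

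For the five-point scales, an effect with 80% power by ANCOVA has about 35–57% under the plan's rule. Direct simulations at 360 per arm, correlation 0.6 to 0.8, with differing baseline levels, cut-points and item noise, gave power of roughly 0.37–0.88 (yes/no) and 0.78–0.99 (ANCOVA). These ranges overlap because they span different settings. Within every setting tried, ANCOVA was the more powerful.

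**Step 4. Ceiling.** Assume 30% vs 38% increase among those able to rise, 600 per arm. If a share c is at the ceiling and scored as not increased, both rates are multiplied by (1 − c).

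| c | Difference | Power, all included | Power, only those able to rise |
|---|---|---|---|
| 0 | 0.080 | 0.83 | 0.83 |
| 0.2 | 0.064 | 0.70 | 0.75 |
| 0.4 | 0.048 | 0.54 | 0.62 |
| 0.6 | 0.032 | 0.37 | 0.46 |

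Most of the loss comes from having fewer people who can change. Restriction recovers only part of it.

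**Step 5. Worsening.** Assume 30% increase in both arms, but 10% vs 18% decrease. The planned test compares 30% with 30% and rejects only at its alpha. A direct test of 10% vs 18% has power 0.98 at 600 per arm and 0.87 at 360.

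**The case against.** **A reader might infer that these are the only analyses planned at T2 and T3.** The documents do not support that. Under Aim 2, Appendix B plans Kruskal-Wallis tests by arm at each time point for feeling informed, trust and misinformation, as part of the mediation work. Its exploratory section looks at positive VCI responses overall and per item. Protocol section 4.5.2 mentions later evaluations without giving a method. Protocol Table 3 also marks future-vaccine intent at all four surveys, whereas Appendix B Table 1 marks it at T1 only. What stands is narrower: within Appendix B, the change rule is the only specified Aim 1 arm comparison at T2 and T3, and none of these other analyses is a full-scale, baseline-adjusted comparison of arms.

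**A reader might infer that harm would be invisible.** It would not. A general downward shift lowers the share who increase. With a −0.25 SD shift, 360 per arm and correlation 0.6, that share fell from about 39–42% to 32–34%, and the planned z-test had 50–62% power, about the same as for a benefit of that size. At T1 the t-tests and the Net Promoter Scores can also show falls. The gap is confined to the Step 5 pattern, where decreases differ and increases do not.

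**Ceiling cases are not a bias.** Randomisation balances them between arms, and screening for worry or no booster makes high baseline confidence less common. The effect is dilution.

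**The power figures use a yardstick the plan does not apply.** Secondary results are read for direction, so power at two-sided 0.05 does not describe their intended use. That is fair, but an imprecise estimate is also a poor guide to direction.

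**The rule is not always the weakest option.** In the Step 3 setting it was slightly more efficient than an unadjusted t-test on follow-up scores (relative efficiency 1.08). The consistent gain comes from keeping the scale and using T0 as a covariate.

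**Yes/no uptake is different.** Increased or not is its natural coding, and true uptake cannot fall. The only issue there is that participants already vaccinated or boosted at T0 are fixed as zero.

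**Conclusion.** The point holds for the scale outcomes: VCI mean, feeling informed, trust and misinformation identification. The rule discards information that the plan itself uses at T1, fixes participants at the T0 maximum as not increased, and gives worsening no category of its own. The direction of the power loss was the same in every setting examined. Its size is assumption-driven, because the documents give no SD, correlation or ceiling share, state a five-point format only for the VCI, and leave the response scales for feeling informed and trust unstated. The power ranges in Step 3 should be read as a bracket and not as a forecast. This is a free improvement to secondary analyses; the primary T1 comparison does not depend on it.

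**What to change.** In Appendix B, before any outcome analysis:

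1. For the scale outcomes, make the main comparison at T1, T2 and T3 the follow-up score adjusted for the T0 score, by ANCOVA at each time or one repeated-measures model.
2. For intent and recommendation categories, use an ordinal or other baseline-adjusted model.
3. For uptake, limit the change analysis to those not yet vaccinated or boosted at T0, or adjust for T0 status.
4. Report increased, unchanged and decreased by arm at each follow-up as a descriptive table.
5. Use one code for a score that did not increase (now 2 in one bullet and 0 in the other), and name the test for the VCI change.

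The cost is SAP wording. T0 values are already collected, no extra participants or surveys are needed, and the descriptive table keeps the share who increased in view.

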3.2 Aims and Objectives

Specific Aim 1: To compare the impact of two interventions delivered online: 1) a dialogue-based webinar using the existing COVID-19 Option Grid conversation aid and, 2) an interactive, dynamic, and multi-component social media website, compared to enhanced usual practice (link to Centers for Disease Control (CDC) vaccine website), on COVID-19 vaccine confidence (primary outcome), and other secondary outcomes among LTCWs (see Figure 1).

Hypothesis 1: Each intervention will be superior to enhanced usual practice at increasing vaccine confidence.

Hypothesis 2: The dialogue-based webinar intervention will be superior to the social media arm at increasing vaccine confidence.

We predict superiority of the dialogue-based webinar intervention based on stronger evidence that exists for dialogue-based approaches and SDM for improving vaccine hesitancy and/or uptake, as compared to social media approaches. While our social media website intervention includes elements of dialogue, this component is more explicit in the webinar intervention (see 'Interventions and control').

Specific Aim 2: To determine if LTCWs' characteristics and other factors mediate and moderate the interventions' impact on vaccine confidence and other secondary outcomes (See Figure 1).

Hypothesis 1: Increased perceptions of feeling informed about the vaccines, identification of vaccine information and misinformation, and trust in vaccine information provided by different sources will explain (mediate) the relationship between the interventions and vaccine confidence, as well as other secondary outcomes.

[figure not shown]
Exploratory: We will conduct exploratory heterogeneity of treatment effects (HTE) analyses to identify whether certain participant characteristics and beliefs moderate the relationship between the interventions and vaccine confidence, as well as other secondary outcomes.

Variables to be explored will include, but are not limited to, vaccination status, religious beliefs, perceived influence of others, age, race, ethnicity and personal experiences with COVID-19.

Specific Aim 3: To explore the implementation characteristics, contexts, and processes needed to sustain and scale up the use of interventions designed to increase vaccine confidence among LTCWs.

Hypothesis 1: Co-developing and adapting the implementation strategy and outcomes with LTCWs and other stakeholders will facilitate implementation.

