4.8 Statistical Analysis

4.8.1 Data Source Accuracy

Initial examination of data will include descriptive statistics and frequency distributions in order to check planned analysis assumptions, identify missing data, and check data source adequacy. This process will also inform any necessary variable re-coding prior to data analysis.

4.8.2 Analyses Corresponding to Trial Aims 1 and 2

All analyses pertaining to study Aims 1 and 2 will be conducted on an intention-to-treat (ITT) basis (i.e. the arm participants were assigned to) and as-treated basis (i.e. whether they engaged with their assigned intervention or control). A detailed data analysis methodology, including planned statistical tests, timepoints for outcome assessment, and treatment of missing data, is included in Appendix B.

For Aim 1, hypothesis 1.1, we will conduct one-tailed tests (superiority analysis) to compare the impact of each of the two intervention arms against the enhanced usual practice arm on primary and secondary outcomes. For Aim 1, hypothesis 1.2, we will conduct a two-tailed test (equivalence analysis) of primary and secondary outcomes between the two intervention arms. While we hypothesize that the dialogue-based webinar intervention (Arm 1) will be superior to the social media website intervention (Arm 2), a finding of superiority, inferiority, or no distinguishable difference will be a valuable finding.

For Aim 2, hypothesis 2.1, our mediation analyses seek to identify the relationship between the interventions, mediator variables, and primary and secondary outcomes. We are interested in whether interventions operate through the mediator rather than directly affecting the outcome. If the results for Aim 1 are non-significant, we will determine whether it is a null effect of the intervention on the mediator or a null effect of the mediator on the outcome. We will determine mediation strength and mechanism generalizability by comparing effects across subgroups.

For Aim 2, hypothesis 2.2, our exploratory moderation analyses (also referred to as heterogeneity of treatment effects (HTE) analyses) seek to understand whether certain participant characteristics and beliefs influence the relationship between the interventions and vaccine confidence, as well as other secondary outcomes. We will explore moderators including (but not limited to) vaccination status, religious beliefs, age, race, ethnicity, perceived influence of others, and personal experiences with COVID-19.

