We hypothesize that increased perceptions of feeling informed about the vaccines, identification of vaccine information and misinformation, and trust in vaccine information provided by different sources will explain (mediate) the relationship between the interventions and vaccine confidence, as well as other secondary outcomes (*Hypothesis 2.1*).

We will also conduct exploratory heterogeneity of treatment effects (HTE) analyses to identify whether certain participant characteristics and beliefs moderate the relationships among each of the interventions and vaccine confidence, as well as other secondary outcomes. Variables to be explored will include, but are not limited to, baseline vaccination status, religious beliefs, perceived influence of others, age, race, ethnicity and personal experiences with COVID-19.

Corresponding analyses

Mediation analysis

We hypothesize that the relationship between participants' assigned trial arm and primary and secondary outcomes will be mediated by the effects of feeling informed, trust in vaccine information, and beliefs about vaccines (measured through questions to determine each participant's ability to correctly classify vaccine information and misinformation). Responses for these three variables will be evaluated at each time point versus outcomes by randomization arm to identify differences by arm using the Kruskal-Wallis test. Significant relationships will be explored for mediation effects in the primary and secondary outcome analyses using the method of Barron and Kenny [2]. If this results in a significant improvement in model prediction, hypothesis 2.1 will be supported.

Heterogeneity of treatment effects/Moderation analysis

To understand how the relationship between study interventions and outcomes are moderated by participant characteristics including age, gender, location (level of regional analysis selected for appropriate granularity), educational attainment, race and ethnicity, health insurance status, health literacy, religiosity, LTCW role, duration of experience in long-term care, extent influenced by others regarding COVID-19 vaccination, personal experiences with COVID-19 and the vaccines, and baseline vaccination status, we will evaluate the primary and secondary outcomes using linear and logistic regression in a mixed-effects model.

Exploratory analyses

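### Hypothesis 2.1 is declared supported on a gain in prediction, with no indirect effect, direction or arm contrast required, so a mediator that moved the wrong way can count as support

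*Combined protocol and SAP*

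**What the plan says.** The hypothesis in Appendix B (Aim 2) names "increased perceptions of feeling informed about the vaccines, identification of vaccine information and misinformation, and trust in vaccine information provided by different sources" as what carries the effect of the interventions on vaccine confidence and on other secondary outcomes. Protocol section 3.2 words the hypothesis in the same way. The hypothesis therefore has a direction. Protocol section 4.8.2 gives the purpose: "We are interested in whether interventions operate through the mediator rather than directly affecting the outcome". It adds that, if Aim 1 is non-significant, the team will work out whether this reflects "a null effect of the intervention on the mediator or a null effect of the mediator on the outcome".

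The Mediation analysis paragraph of Appendix B then sets three steps:

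1. A screen: "Responses for these three variables will be evaluated at each time point versus outcomes by randomization arm to identify differences by arm using the Kruskal-Wallis".
2. A method for what passes: "Significant relationships will be explored for mediation effects in the primary and secondary outcome analyses using the method of Barron and Kenny".
3. The decision: "If this results in a significant improvement in model prediction, hypothesis 2.1 will be supported".

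No alpha, sign, pair of arms, confidence interval or indirect effect is attached to any step. The Multiple testing paragraph of Appendix B covers the three primary tests and says that secondary outcomes will be read in aggregate. It does not mention mediation.

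**The concern.** The hypothesis and the rule that decides it have different nulls. The hypothesis fails if there is no positive effect of an intervention through the mediator. The decision sentence fails only if the mediator is unrelated to the outcome. Trust and feeling informed can be expected to go with vaccine confidence whatever the interventions do, so the decision step alone says little about mechanism. The screen does bring in the trial arm, but it responds equally to a rise or a fall and does not say which arm differs from which.

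Aim 2 is meant to explain why an intervention works. Section 3.2 labels only the heterogeneity analyses exploratory, so Hypothesis 2.1 is a stated hypothesis with a declared outcome. Followed literally, the plan could report increased trust as the explanation in a trial where trust fell.

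**Working it through.** **Inputs from the documents.** 600 per arm, 1:1:1. After 40% attrition: 600 × (1 − 0.40) = 360 per arm. Three mediators and three follow-up waves. The plan gives no mediation figure to reproduce. As a check on the arm sizes, 600 per arm with an 8-point difference at two-sided 0.05 gives power 0.79–0.83 for assumed control rates of 0.30–0.60, consistent with the stated 80%. With 360 per arm and 10 points it is 0.77–0.80.

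**Assumptions not in the documents.** Mediator–outcome log-odds of 0.2–1.2 per SD, arm–mediator shifts of 0 or ±0.2 SD (also −0.1 and −0.3), and every test at 0.05.

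**What each step tests.** For a mediator M and outcome Y, with arm indicators A1 and A2 and Arm 3 as reference:

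- M = a0 + a1·A1 + a2·A2 + error
- logit P(Y = 1) = c0 + c1·A1 + c2·A2 + b·M

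The hypothesis for Arm k versus Arm 3 needs ak > 0 and b > 0. The screen, read as mediator by arm, tests a1 = a2 = 0. The decision sentence, read as a likelihood-ratio test of adding M, tests b = 0. With a1 = a2 = −0.2 and b = 0.8, the product on the logit scale is about −0.2 × 0.8 = −0.16. This is opposite to the hypothesis, yet both nulls are false and both tests tend to reject.

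**Simulation.** Standardised mediator, 800–1,500 trials per case. Binding causal steps means screen and criterion plus a significant total effect, a significant arm–mediator path and an attenuated arm coefficient, for Arm 1 versus Arm 3. The two-path test requires both paths to be significant in the hypothesised direction for that contrast. Entries are the percentage of trials declaring support.

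| Case | Criterion alone | Screen + criterion | Binding causal steps | Directional two-path test |
|---|---|---|---|---|
| No arm moves M (600 or 360 per arm) | 88–100 | 3–6 | 0–1.2 | 1.4–3.5 |
| Both lower M by 0.2 SD, no direct effect, 600 | 100 | 95–96 | 7–21 | 0 |
| Same, 360 | about 100 | 75–81 | 5–14 | 0 |
| Both lower M by 0.2 SD, direct log-odds +0.6, 600 | 100 | 95 | 0 | 0 |
| Same, 360 | 100 | 78 | 0 | 0 |
| Both raise M by 0.2 SD (b = 0.8, direct log-odds +0.2), 600 | 100 | 94 | 74 | 93 |
| Same, 360 | 100 | 78 | 43 | 78 |

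A second simulation with five-level mediators gave 91% (600) and 77% (360) for screen plus criterion when both interventions lower M by 0.2 SD. For shifts of −0.1 to −0.3 SD, screen plus criterion ranges from 22% (360 per arm, −0.1) to 100% (600 per arm, −0.3). With binding steps and no direct effect, counting support in either intervention contrast gives 22–32% at −0.2 SD.

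**Repeated testing.** With independent tests at 0.05, the chance of at least one false pass is 1 − 0.95³ = 0.143 for three mediators at T1, and 1 − 0.95⁹ = 0.370 for three mediators at T1–T3. With assumed correlations within and between waves, the simulated figures are 10–14% and 22–34%.

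**The case against.** The strongest reply is that the decision sentence does not stand alone. It follows an arm-based screen and the Baron and Kenny method, and its opening words point back to both. Screen plus criterion is close to a joint test of the two paths. If the causal steps bind, false support with no arm–mediator effect is about 1% or less per test, and a wrong-way mediator with a positive direct effect is almost never called support. Appendix B also compares these three variables between arms by t-test and scores their change from baseline as an increase or not, so a fall in trust would be visible in the same report. Section 4.8.2 promises to separate the paths when Aim 1 is non-significant.

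Much of this stands, and it rules out stronger readings that a reader might infer:

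- *Mediation will be declared almost always where none exists.* The 88–100% belongs to the criterion in isolation. The screen brings it to about 5% per mediator and wave. The screen sentence is loosely worded, but a comparison of mediators by arm is its natural sense.
- *The 22–34% shows a wrong null.* It comes from unadjusted repeated testing. Counting T0 as a screening wave would raise it, but Table 1 of Appendix B lists these variables as outcomes at T1 and uses T0 for change from baseline.
- *Support is false when only Arm 2 raises the mediator.* Mediation for Arm 2 versus Arm 3 is then real. What is missing is the label saying which contrast was supported.

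The reply does not repair the rule itself. Appendix B says only that relationships will be explored with the causal steps, and then sets its own criterion. A required total effect also sits badly with mediation work planned for a non-significant Aim 1. The other analyses show direction but do not change what counts as support.

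**Conclusion.** The point holds as a defect in the decision rule. The rule is not tied to the indirect effect, its direction or a contrast, so support for a directional hypothesis can rest on opposite evidence. The size depends on a question the plan leaves open. If the causal steps do not bind, a 0.2 SD fall in the mediator in both interventions is declared support in about 91–96% of trials at 600 per arm and 75–81% at 360. If they bind, this is about 0% with a positive direct effect and roughly 5–32% without one. In that last situation the interventions lower confidence through the mediator: there is mediation, but not the kind hypothesised. With no arm–mediator effect the error is near nominal for one test and reaches about 22–34% over nine.

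All these rates rest on assumed mediator–outcome effects and 0.05 tests, because the plan gives neither. The primary comparison is unaffected.

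**What to change.** Replace the support sentence with a rule for each mediator and each of Arm 1 versus Arm 3 and Arm 2 versus Arm 3. Hypothesis 2.1 is supported for that mediator and contrast only if the indirect effect on the T1 primary outcome is in the hypothesised direction, with a confidence interval above zero. A simpler form of the same requirement is that both paths are significant in the hypothesised direction. In addition:

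- State the alpha and a multiplicity adjustment over 3 mediators × 2 contrasts = 6 tests, for example Holm.
- Treat secondary outcomes and other waves as descriptive.
- Use T0 values as covariates and not as a screening wave.
- State the assumption of no unmeasured mediator–outcome confounding.
- Keep Kruskal-Wallis as descriptive only.

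The cost is SAP wording and an analysis of data already being collected. Support will be declared less often. Before multiplicity adjustment, the directional two-path test has power of about 93% (600 per arm) or 78% (360) for a true +0.2 SD shift at an assumed log-odds of 0.8 per SD. Adjustment will lower these figures; by how much was not calculated.
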